	Screen	1	2	3	4	5	6	7	8	9	10	11	12	13	14	15	16	17	18	19	20	21	22	23	24	25	26	27	28	29	30	31	32				
ALL PATIENTS																																					
Check inclusion / exclusion criteria	X																																				
Informed consent	X																																				
Optional blood sample (check consent)	X																																				
Request stored pathology samples (check consent)	X																																				
Offer OxMdG or IrMdG	X																																				
Send sample of primary cancer for KRAS analysis	X																																				
Randomisation	X																																				
Calculate GFR (if < 50 ml/min, measure GFR)	X																																				
QoL questionnaire	X																																				
CT scan (Chest, abdo, pelvis or equiv.)	X*																																				
Tumour marker (CEA or other)	X*																																				
Liver resection surgery	X*																																				
Collect pathology samples (check consent)																																					
OxMdG and IrMdG PATIENTS																																					
Check adverse events		X																																			
Clinical evaluation		X																																			
RECIST response	X																																				
NCI CTC scores		X																																			
WHO PS		X																																			
FBC, U&Es, LFTs, magnesium**		X																																			
Chemotherapy - folinic acid		X																																			
Chemotherapy - Oxaliplatin (OxMdG) or Irinotecan (IrMdG)		X																																			
Chemotherapy - 5FU		X																																			
Chemotherapy - Cetuximab (if applic.)		X																																			
Return data to UoSCTU		X																																			

Results from FBC, U&Es, LFTs required before patient attends baseline visit; delay between baseline visit to week 1 visit must be < 3 weeks if clinically acceptable; * = procedure may be performed at screening or baseline but must be within 6 weeks prior to chemotherapy; † = if raised at baseline; ** = measure in all patients showing possible symptoms of hypomagnesaemia; QoL = quality of life; NCI CTC = national cancer institute common toxicity criteria; WHO PS = world health organisation performance status; follow-up schedule (including CT scans) described section 11 should be followed after the treatment phase

4. Introduction

Background

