This protocol has been evaluated in a large phase III trial including patients with metastatic colorectal cancer¹². Please see appendices I-IV for details of the chemotherapy regimens.

5. Aims

The **primary aim** of the New EPOC trial is to determine whether the addition of Cetuximab to Oxaliplatin plus modified de Gramont or Irinotecan plus modified de Gramont combination chemotherapy results in improved progression free survival when compared with combination chemotherapy alone in patients who do not possess a kRAS mutant genotype confirmed by laboratory analysis.

Secondary aims

1. To evaluate overall survival.
2. To evaluate quality of life.
3. To compare the experimental arm in terms of cost effectiveness in a UK treatment setting
4. To determine whether the addition of Cetuximab to combination chemotherapy as above results in improved progression free survival when compared with combination chemotherapy alone in patients who possess the kRAS-wt genotype confirmed by laboratory analysis

Translational research aims

1. To assess the difference in progression free survival with chemotherapy plus Cetuximab for all patients irrespective of EGFR detectability in tumour tissue on IHC; for patients with detectable EGFR and for those with undetectable EGFR.
2. To determine, from DNA extracted from peripheral blood, the impact of individual variance in DNA repair capacity on tumour response, progression free survival and grade 3/4 toxicities.
3. To determine, from DNA extracted from peripheral blood, whether variance in the enzymes involved in the metabolism, transport and cellular targets of the drugs used affects tumour response, progression free survival and grade 3/4 toxicities.
4. To determine the effect of Cetuximab on the expression profile of hepatic metastases.

6. Outcome measures

Primary: progression-free survival.

Secondary: pre-operative response, pathological resection status, peri-operative safety findings, overall survival, EQ-5D, EORTC QLQ-C30, EORTC QLQ-LMC21, measures for cost effectiveness.

Definitions

Progression-free survival (PFS) is defined as the time from randomisation to first recurrence/disease progression or death, whichever occurs first. Patients not experiencing recurrence/progression/death will be censored at the date of the last follow-up examination. PFS will be assessed as follows:

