- The ambulatory technique for OxMdG and IrMdG is described in AAppendix III. These regimens may also be given on an inpatient basis, but investigators are urged to use outpatient ambulatory treatment whenever possible.

9.b Treatment duration and breaks

- **Arm A (Control, OxMdG / IrMdG):** These patients will receive 12 weeks of pre-operative and 12 weeks of post-operative chemotherapy dependent on cumulative toxicity, post-surgical performance status or because of patient choice to stop chemotherapy. Patients in this arm should continue on treatment with no more than a three week interval off treatment for any reason although the post surgical interval can be 6 weeks. *The cumulative toxicity that is most likely to occur is the neuropathy associated with Oxaliplatin, which increases in incidence from about 12 weeks duration of therapy. If this occurs, patients may continue on the fluorouracil component of the regimen with dose increment as indicated in Appendix I.* If the neuropathy resolves to < grade 1 the Oxaliplatin may be reintroduced cautiously at the investigator's discretion.
- **Arm B: OxMdG / IrMdG plus Cetuximab:** These patients will receive chemotherapy as Arm A above plus Cetuximab. Patients in this arm should continue on treatment with no more than a three week interval off treatment for any reason although the post surgical interval can be 6 weeks. Cetuximab will be continued if chemotherapy is stopped because of toxicity or patient choice, but should be discontinued on recurrence or unacceptable Cetuximab toxicity. Full details of Cetuximab administration and dose reduction and delays are given in Appendix I.

9.c Surgery

The liver resection is carried out **at the earliest 4 weeks** after the last administration of chemotherapy and Cetuximab, and within 2 to 6 weeks of CT scanning at the end of the pre-operative period. Patients who progress during the first 12 weeks of chemotherapy and who are still operable should be considered for surgery. However these patients are unlikely to be salvaged with surgery and consideration should be given to second-line chemotherapy. In addition, the patient must have completely recovered from side effects, the general condition according to WHO grade must be ≤ 1 and liver function must be adequate for liver surgery.

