11.e Every chemotherapy cycle (day 1, or up to 3 working days before)

1. Clinical evaluation (doctor/nurse), to include NCI toxicity scores from previous cycle (see Appendix XI) and current WHO PS (see Appendix VII)
2. Check FBC, U&Es, and LFTs (see regimen details in Appendix I for critical values).
3. Measure and record magnesium levels.
4. Recalculate drug doses if patients' weight has changed by more than 10%, or follow local policy.
5. Record Cetuximab administration details for patients in Arm B.
6. These data should be collated on the **Treatment Form** which is returned to UoSCTU every 6 weeks (i.e. after every 3 cycles of OxMdG or IrMdG)

Patients should also complete QoL questionnaires during both pre- and post-operative chemotherapy at the beginning of cycle 4 with OxMdG and IrMdG.

11.f Surgery

Surgical data will be recorded on the surgery form and returned to UoSCTU within four weeks of the date of surgery. Investigators should make local arrangements to ensure that facilities to snap-freeze samples are available during surgery (if possible). Pathology samples (normal and tumour tissue) obtained following liver resection surgery should be requested and sent to the Cancer Sciences Tissue Bank, Southampton (see section 11c) for those patients who have given consent.

11.g After the end of treatment

After completion of study treatment patients will be followed up with the following tests and procedures every 3 months for 2 years, and every 6 months thereafter until progression for a further 3 years and/or death, using the **Progress report & follow-up form**:

1. Clinical examination.
2. Chest, abdomen and pelvis CT scan (or equivalent imaging). Chest x-ray only to be performed if chest CT not available.
3. A QoL form should also be completed every 3 months for the first year and every 6 months thereafter.
4. Magnesium levels should be measured 6-8 weeks after the last dose of Cetuximab and at intervals until hypomagnesaemia has resolved.
5. Documentation of survival status and further anticancer treatments will be done. All deaths should be reported to UoSCTU using the Death CRF.

Patients who progress whilst in follow-up should come off protocol follow-up but treatment and care outcome data should still be collected. The follow-up only form should be completed at the same study time points.

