- Dose modifications for grade 3 toxicity are summarised on the algorithm below. For CTC grade 1 or 2: continue treatment with Cetuximab. If a patient experiences grade 3 skin toxicity (rash effects $> 50\%$ of body surface area), Cetuximab therapy may be delayed for up to 14 days without changing the dose level. If grade 3 skin toxicity occurs for a second and third time, Cetuximab therapy may again be delayed for up to 14 days with concomitant dose reductions to 400 mg/m^2 and then 300 mg/m^2 . Cetuximab dose reductions are permanent. Patients must discontinue Cetuximab if more than 2 consecutive infusions are withheld or grade 3 skin toxicity occurs for a fourth time despite appropriate dose reduction. If the toxicity resolves to grade 2 or less by the following treatment period, treatment may be resumed.
- The investigator should also consider concomitant treatment with topical and oral antibiotics. Grade 1 acneiform eruption: consider treatment with topical antibiotics (e.g. Topical Metronidazole or Erythromycin). Systemic antibiotics (e.g. a second generation tetracycline such as Doxycycline 100mg po daily) should be considered for grade 2 acneiform eruption, and are mandatory for grade ≥ 3 reactions. The threshold for referral to the dermatology clinic should be planned locally but all patients with grade ≥ 3 reactions and probably all with grade 2 reactions should be referred for advice and management. If pruritus occurs an oral antihistamine is advised. Dry skin often occurs (and may contribute to pruritus) general advice on replacing soap with oil for washing, avoidance of hot water for baths or showers and use of emollient creams are beneficial; topical corticosteroids can be used according to local practice. Fissures may occur in dry skin and topical dressings (e.g. hydrocolloid dressings and as advised by your dermatologist) are helpful.

- Colloidal oatmeal preparations (Aveeno, Nature's Gate) can be effective if applied at least 3 times daily⁴⁸. These are available at chemists or on the internet.

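### The follow-up CT schedule that dates PFS events starts at completion of study treatment, a date that section 9.b can make later in Arm B when chemotherapy stops early

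*Protocol*

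**What the plan says.** Section 6 sets the time origin of the primary endpoint: "Progression-free survival (PFS) is defined as the time from randomisation to first recurrence/disease progression or death, whichever occurs first".

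Section 11.g sets the scans that detect recurrence after treatment: "After completion of study treatment patients will be followed up with the following tests and procedures every 3 months for 2 years", then 6-monthly for a further 3 years. The listed tests include "Chest, abdomen and pelvis CT scan (or equivalent imaging"). The footnote to the section 3 table points to the same schedule: "follow-up schedule (including CT scans) described section 11 should be followed after the treatment phase".

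Section 9.b describes the treatment course. For Arm A: "These patients will receive 12 weeks of pre-operative and 12 weeks of post-operative chemotherapy dependent on cumulative toxicity", with post-surgical performance status and patient choice as further reasons to stop. Arm B receives the same chemotherapy plus cetuximab, with one additional rule: "Cetuximab will be continued if chemotherapy is stopped because of toxicity or patient choice, but should be discontinued on recurrence or unacceptable Cetuximab toxicity". Section 2 describes 12 weeks of chemotherapy, surgery and a further 12 weeks.

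**The concern.** Recurrence found on routine imaging can be dated only at a scan. If scan dates follow a post-randomisation event that one arm reaches later by rule, recorded PFS can differ between arms with no difference in disease.

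Take two patients who stop chemotherapy at the same visit. If stopping completes study treatment, the Arm A patient enters 3-monthly scanning at once. The Arm B patient, still on cetuximab, does not. Section 9.b ends that cetuximab only at recurrence or unacceptable toxicity. Read literally, the Arm B patient could have no follow-up CT scheduled under 11.g until cetuximab ends.

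The endpoint is primary, the trial is open-label, and section 18 specifies an unadjusted Cox regression, which takes recorded dates at face value.

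**Working it through.** **Design figure (section 18).** HR 0.68, 80% power, two-sided 5%, 1:1 allocation. Schoenfeld events = 4 × (1.960 + 0.842)² / (ln 0.68)² = 4 × 7.85 / 0.1487 ≈ 211.1, rounded up to 212. This matches the stated target, so SE(log HR) ≈ 2/√212 = 0.137.

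**Where the anchor falls.** The shortest planned course is 12 weeks of chemotherapy, 4 weeks to surgery, 4 weeks to restart (both minima from section 9.c) and 12 weeks more: 12 + 4 + 4 + 12 = 32 weeks. The first follow-up scan, 3 months later, is near week 32 + 13 = 45 in both arms.

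**What early stopping does.** If an Arm A patient stops d weeks early and this counts as completion, the first follow-up scan moves to week 45 − d. An Arm B patient who stops chemotherapy at the same point but stays on cetuximab to week 32 is still scanned at week 45. The gap is up to 12 weeks within the post-operative block, and 32 − 12 = 20 weeks if no post-operative chemotherapy is given.

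**Effect on the hazard ratio.** Simulation with exponential PFS (control median 15 months, section 18), one scan at week 13, then the 11.g schedule from each patient's completion date. Each event is dated at the next scan, and the Cox model uses Efron ties. The share stopping early is assumed equal in both arms. Observed HR when the true HR is 1:

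| Weeks early (d) | 20% stop early | 40% stop early |
|---|---|---|
| 3 | 0.983 | 0.966 |
| 6 | 0.986 | 0.976 |
| 9 | 0.996 | 0.993 |
| 12 | 0.999 | 1.003 |
| 16 | 0.992 | 0.979 |
| 20 | 0.998 | 0.996 |

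With one common schedule the result is 0.998, which shows the size of the simulation error. The effect does not grow steadily with d: a 12-week shift is almost a whole 3-month interval, so the two sets of scan dates nearly line up again.

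- If Arm A stops 12 weeks early and the matched Arm B patients complete 26 weeks after week 32, the HR is 0.987 (20%) or 0.974 (40%).
- When the true HR is 0.68, the table's scenarios give 0.662-0.682, against 0.683 on a common schedule.
- A separate simulation, using both the exponential curve and the section 18 baseline PFS (67/46/35%), with stops of 6-12 weeks, gives 0.985-0.99, or 0.99-1.00 with an end-of-treatment scan.

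**What this does to the test.** At the extreme of 0.966, the shift is ln 0.966 / 0.137 ≈ −0.25 SE, so the one-sided error in favour of Arm B rises from 2.5% to about 4.4%. At 0.985-0.99 the shift is 0.07-0.11 SE.

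**The case against.** The strongest reply is that the protocol never says early stopping completes study treatment. Section 13.a calls it withdrawal from trial treatment, and the section 3 footnote starts the scan schedule after a treatment phase set out in numbered weeks to 32. If every patient's follow-up starts from that nominal phase, the difference between arms disappears. That reading is available, but 11.g does not state it, and sites could apply either.

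Other points stand and limit the finding:

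- Section 9.b names oxaliplatin neuropathy as the likeliest cumulative toxicity and lets such patients continue on fluorouracil, so this cause need not end treatment early in either arm.
- The CT row of the section 3 table is not legible in the text available, so an end-of-treatment scan may exist and would narrow the gap.
- Clinical evaluation at every cycle may reveal some progressions before a scheduled scan.

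A reader might infer more: that Arm B as a whole is scanned later, so that the bias always favours cetuximab and reaches an HR of 0.95-0.97. The documents do not support this. Patients who complete the planned course have the same anchor. The larger figures need Arm B treatment to end 2-4 weeks later on average, which no passage gives. The rash and hypomagnesaemia text in Appendix I says that "Cetuximab therapy may be delayed for up to 14 days without changing the dose level", but not that the course is extended. Nor is the direction fixed: if more Arm B patients stopped all treatment because of added toxicity, their scans would come earlier.

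**Conclusion.** The point holds as an arm-dependent weakness in how the primary endpoint is ascertained, not as a demonstrated bias of any size. Scan timing hangs on a post-randomisation date that section 9.b can set differently by arm, and no legible passage offsets this. The null HR is likely to be about 0.97-1.00, and close to 1.00 with an end-of-treatment scan, against a design HR of 0.68. This rests on an assumed 20-40% stopping early, on early stopping counting as completion, and on similar chemotherapy stopping in both arms. The protocol supplies none of these. Even if stopping differed between arms, detection time would still depend on the treatment course, and that is the reason to change it.

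**What to change.** In section 11.g, set PFS imaging at fixed times from randomisation, with a stated window, the same in both arms whatever the treatment or resection status, and keep the pre-operative scan. One example is months 12 to 33 every 3 months, (33 − 12)/3 + 1 = 8 scans, then months 39 to 69 every 6 months, (69 − 39)/6 + 1 = 6 scans. The total of 14 equals the present 24/3 + 36/6, so the radiation statement in 11.g need not change.

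Reconcile sections 2, 9.b and 11.g on what counts as completion of study treatment. This is needed for the imaging schedule and does not require the review to choose a treatment rule.

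Section 14 expected recruitment to end in December 2012, and section 26 lists an amendment dated October 2017, so a new schedule may reach few patients in this trial. For those already scanned, report scan times by arm and add an interval-censored sensitivity analysis of PFS. This mitigates unequal scan times but does not replace matched ones.

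Cost: one schedule amendment and one additional analysis. Some scans would no longer coincide with end-of-treatment visits. Starting at month 12 also lengthens the first gap after the pre-operative scan, from 45 − 13 = 32 weeks to 52 − 13 = 39 weeks on the shortest course, if no treatment-phase scan falls between. Starting at month 9 avoids that but adds one scan.

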In patients with resected metastases (R0 or R1 or R2), PFS will be considered to be the time from randomisation to the first of the following events:

- Recurrence/disease progression after surgery
- Death

In patients with unresected metastases, PFS will be considered as the time from randomisation to the first of the following events:

- Disease progression (whenever it occurs, before or after the planned surgery date)
- Death

Overall survival is defined as the time interval between the date of randomisation and the date of death. Patients who are still alive when last traced will be censored at the date of last follow-up.

Pre-operative response: evaluation of the activity of study treatment on hepatic metastases will be done according to the RECIST criteria (see Appendix V), after the end of the pre-operative treatment period by abdominopelvic computed tomography (CT) scan or magnetic resonance imaging (MRI) ideally within 1 week but not longer than 2 weeks. As patients will undergo surgery

within 2 to 4 weeks of CT scanning at the end of the pre-operative period, the 4 week confirmation does not apply for patients who achieve their first response at this time point.

A pre-operative safety finding will be if >6 weeks delay of surgery due to study treatment-related toxicity, with the delay being measured between the end of pre-operative chemotherapy (last day of last cycle) and surgery.

Pathological resection rate: following surgery, the pathologist will assess the resection as R0, R1 or R2. The rates of R0, R1 and R2 resections will be presented.

Peri-operative safety findings: any of the following events provided they are due to a severe surgery-related complication (i.e. wound infection, intra-abdominal infection, severe sepsis.):

- Prolongation of hospitalisation (discharge >20 days after surgery)
- Re-hospitalisation within 30 days of surgery
- Re-operation under general anaesthesia within 30 days of surgery (excluding secondary surgery after R1 resection)
- Death during surgery or within 30 days of surgery
- Other severe pre- or post-operative complications within 30 days of surgery:
 - Surgery-associated bleeding with replacement ≥ 4 units of erythrocyte concentrates
 - Biliary fistula for more than 10 days with a discharge of >100 mL/day
 - Transient liver failure, defined as a bilirubin level >10 mg/dL lasting >7 days
 - Renal failure requiring dialysis

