The type and extent of liver resection should be decided at time of randomisation and should include all the areas that have contained tumour even when there is marked tumour shrinkage or a complete radiological response. It is accepted by most liver surgeons that the benefit of neoadjuvant chemotherapy is that it may increase the surgeons ability to achieve clear margins. When previously undetected deposits are discovered at surgery or if the tumour is larger than expected, liver resection should be adapted to ensure complete tumour resection wherever possible.

Before the beginning of the liver resection (after abdominal incision), extrahepatic involvement of the abdomen must be excluded by inspection and palpation and frozen section histological examination of suspicious lesions. Intra-operative ultrasonography is suggested to detect and localize any additional metastases but is not mandatory.

A curative resection of the metastases with a clearance of ≥ 1 cm of normal parenchyma should be the aim. However metastases will be considered resectable even if the clearance is less than 1 cm provided complete macroscopic resection of liver metastases is possible. Whether anatomical liver resection or wedge resection or a combination of the two is carried out depends on the localization of the metastases. The surgical technique, including vascular isolation, use of technology is left to each surgeon's discretion. The technique used should be noted on the correct form and blood loss and extent of resection detailed. Post-operative follow up will be recorded and serious complications will be reported within one month after surgery to allow a direct comparison.

Post-operative study treatment should **start 4 weeks** after surgery (not earlier); however, post-operative study treatment may be delayed until 8 weeks after surgery, at the latest. The rationale for any delays must be documented in the CRF.

9.d Other anticancer treatment modalities

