All SAEs must be reported immediately by the Investigator (Consultant responsible for the patient) to UoSCTU UNLESS the SAE is specified in section 12.b. Investigators should notify UoSCTU of all SAEs occurring from the time of randomisation until 30 days after the last protocol treatment administration. SUSARs occurring after this 30 day period must be reported to UoSCTU following the same procedure. A completed SAE form for all events requiring immediate reporting should be faxed to the UoSCTU within 24 hours of identification of the event. This should be followed by further reports giving additional relevant information as required. Other adverse events should be recorded on the appropriate CRF.

Death as a result of disease progression and other events that are primary or secondary outcome measures are not considered to be SAEs and should be reported in the normal way, on the appropriate CRF.

SAEs will be recorded in the medical notes and the CRF returned to UoSCTU in a timely manner. UoSCTU is responsible for, and will report SUSARs (Suspected Unexpected Serious Adverse Reactions) and other suspected SARs to the regulatory authorities (MHRA, competent authorities of other EEA (European Economic Area) states in which the trial is taking place) and the relevant ethics committees as follows:

- SUSARs which are fatal or life-threatening reported not later than 7 days after the sponsor is first aware of the reaction. Any additional relevant information reported within a further 8 days.
- SUSARs that are not fatal or life-threatening reported within 15 days of the sponsor first becoming aware of the reaction.
- Suspected SARs (expected and unexpected) listed and reported annually.

All serious adverse drug reactions will also be reported by the clinician caring for the affected patient to the MHRA Committee on Safety of Medicines using the yellow card scheme.

12.b SAEs not requiring immediate reporting

The most recent version of an agent SpC should be accessed at www.medicines.org.uk. A file note detailing this process is filed in the investigator site file. SAEs that are expected with these agents and do not require immediate reporting in this trial are documented in the SpC.

12.c Evaluation of SAEs

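### Section 12.a exempts every outcome event from SAE status, so surgery-related deaths and organ failures bypass 24-hour reporting, and the 30-day reporting window is not tied to surgery

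*Protocol*

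**What the plan says.** Protocol section 12 defines as serious any adverse event that is fatal, life-threatening or involves hospitalisation. Section 12.a requires a faxed SAE form within 24 hours of identifying an event that needs immediate reporting. It then makes an exception: "Death as a result of disease progression and other events that are primary or secondary outcome measures are not considered to be SAEs". Excepted events go on the ordinary CRF.

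Section 6 gives the secondary outcomes as "pre-operative response, pathological resection status, peri-operative safety findings, overall survival", followed by the quality-of-life and cost-effectiveness measures. The primary outcome, PFS, is the "time from randomisation to first recurrence/disease progression or death, whichever occurs first". The peri-operative safety findings include "Death during surgery or within 30 days of surgery", re-operation, dialysis, liver, respiratory and cardiac failure, thromboembolism, and severe study-treatment toxicity that ends all drugs or is fatal. A proviso introduces the list: the event must be due to a severe surgery-related complication.

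For surgical harm, section 9.c says "serious complications will be reported within one month after surgery to allow a direct comparison", and section 11.f has the surgery form "returned to UoSCTU within four weeks of the date of surgery". Section 11.g puts deaths on a Death CRF and gives no deadline.

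SAE notification runs from randomisation "until 30 days after the last protocol treatment administration". Resection is at the earliest 4 weeks "after the last administration of chemotherapy and Cetuximab, and within 2 to 6 weeks of CT scanning" (section 9.c). Post-operative treatment starts between 4 and 8 weeks after surgery.

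**The concern.** An exemption for outcome events usually keeps progression and death from progression, which are expected and counted anyway, out of the expedited stream. Here the clause covers every primary and secondary outcome, and one secondary outcome is itself a list of serious harms. A site that follows 12.a to the letter would not send an SAE form for a post-operative death from sepsis or for post-operative renal failure needing dialysis.

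The consequence goes beyond timing. The causality, seriousness and expectedness assessment in section 12.c starts from an SAE. An event declared not to be one has no stated way into that assessment, and the 7-day clock for a fatal SUSAR starts only when the sponsor becomes aware. Cetuximab is unlicensed for this first-line use (section 10.a), and the trial gives it before liver surgery. Whether it contributed to a surgical complication is the kind of question that prompt central review exists to ask.

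The window adds a second uncertainty. It is counted from the last treatment administration and not from surgery, and the patients least likely to restart treatment are those whom surgery has harmed.

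**Working it through.** The protocol states no figure to reproduce here. The check is a comparison of sections, followed by day arithmetic.

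**1. Which events the exemption reaches**

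- *Death in surgery or in the following 30 days, due to a severe surgery-related complication:* a listed secondary outcome (section 6), so exempt under 12.a. Section 12 would make it an SAE because it is fatal. The two conflict.
- *Listed liver, renal, respiratory or cardiac failure, same proviso:* exempt under 12.a. Section 12 would make it an SAE wherever it is life-threatening or prolongs hospitalisation. The two conflict.
- *Organ failure from drug toxicity with no surgical complication:* the proviso keeps it off the section 6 list, so it stays an SAE.
- *Toxic death:* the proviso literally governs the toxicity item too. However, any death is a PFS and OS event, so a literal reading of 12.a still exempts it. The wording of 12.a also points the other way (see the objection).

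**2. Reporting routes**

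- SAE route: 24 hours from identification.
- Serious surgical complications: within one month.
- Surgery form: within four weeks, 4 × 7 = 28 days.
- Death CRF: no stated limit.

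A form due by day 28 after surgery can fall before the 30-day endpoints are complete (30 − 28 = 2 days short). It cannot hold the finding of a restart delayed beyond 8 weeks (56 days), so other forms must contribute.

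**3. The window if only drug administration counts**

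Let day 0 be the last pre-operative drug administration and S the day of surgery.

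- Window closes: day 30.
- Earliest surgery: S = 4 × 7 = 28.
- Post-operative days covered = max(0, 30 − S). At S = 28 this is 2; at S = 30 or later it is 0.
- The 30 post-operative days end at 28 + 30 = day 58, leaving 58 − 30 = 28 of them uncovered.
- Later surgery is permitted. Section 6 allows the CT up to 14 days after pre-operative treatment. Counting those days from day 0, surgery can fall as late as 14 + 28 = day 42 (section 6, up to 4 weeks after CT) or 14 + 42 = day 56 (section 9.c, up to 6 weeks). Coverage is then 0 days.
- Earliest post-operative treatment: 28 + 28 = day 56. A patient who dies in the first four weeks after surgery therefore always has the pre-operative dose as the last one.

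For patients who do restart, the window runs through surgery to 30 days after their last post-operative dose.

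**4. The window if resection counts**

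The window closes on day S + 30, and all 30 post-operative days are covered. The range for a patient who never restarts is therefore 0 to 2 days on one reading and 30 on the other.

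**The case against.** Several points on the other side are sound.

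- A reader might infer that every death not due to progression is exempt. The literal text allows this through PFS and OS, but 12.a names only death from progression, and those words would do no work if all deaths were exempt. The narrower intent is more plausible. The point stands without this reading, because surgery-related deaths are exempt by a separate path, as peri-operative safety findings.
- A reader might infer that all organ failure escapes SAE status. The section 6 proviso rules that out.
- A reader might infer that drug-related harm is hidden from regulators. The protocol keeps other duties: SUSARs remain reportable even after the 30 days, investigator reports of suspected SARs are reviewed immediately (12.c), and clinicians send serious drug reactions by yellow card (12.a). These limit the harm. They depend on the site suspecting a drug cause, and the central review that would test that suspicion starts from an SAE.
- A reader might infer a delay to the DMEC. Section 24 says only that it meets at least annually and advises on the frequency of reviews; nothing ties its information to the 24-hour form.
- The 2-day figure is conditional. Surgery sits within the study regimen in section 2 and under the treatment heading of section 9, so resection can fairly be read as protocol treatment. Against that, section 9.c uses the word administration for the drugs. The protocol does not settle it. While restart is still planned, a site also cannot know that the pre-operative dose was the last.

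No endpoint or analysis changes, and the outcome data still reach the CRFs.

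**Conclusion.** The contradiction is real. As written, 12.a takes peri-operative deaths and the listed organ failures, when due to a severe surgery-related complication, out of SAE status, against the section 12 definition. The loss is prompt sponsor awareness (up to four weeks or a month, or no stated limit, instead of 24 hours) and the 12.c review. It is not loss of the data or of the retained drug-reaction duties. Exemption of toxic deaths follows only from a literal reading that was probably not intended.

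The window is a separate ambiguity. At most 2 post-operative days are covered if administration means drug and the patient never restarts, and all 30 if resection counts. The documents do not support stating the short window as fact, but a reporting rule should not permit both readings.

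One limit applies to any correction: section 12.b separately spares SAEs expected under the SpC from immediate reporting. Those events remain SAEs, and that rule is not in question here.

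**What to change.** Reconcile section 12.a with sections 6 and 12:

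1. Limit the exemption to disease progression and death due to disease progression, and remove the reference to outcome measures in general. State that peri-operative safety findings meeting the SAE definition, and all other deaths, follow the SAE route while also being recorded as outcomes.
2. State that the reporting window runs to 30 days after the later of the last drug administration and liver resection.
3. Optionally, set the surgery form's due date after day 30, or name the form that completes the 30-day endpoints.

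The cost is a short amendment to 12.a (and to 11.f if item 3 is taken up) and a modest increase in SAE forms. Sample size, endpoints and analysis are unaffected.
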